## 3.2. Definitions of Endpoints

### 3.2.1. Complete TMA Response

Complete TMA Response is defined as the normalization of hematologic parameters (platelet count and LDH) and  $\geq 30\%$  improvement in estimated glomerular filtration rate (eGFR) from baseline (Table 5).

For Complete TMA Response, participants must have met all 3 TMA response parameters, with each parameter meeting the requirement at 2 separate assessments obtained at least 24 hours apart, and any measurement in between. The first laboratory value will be assessed based on central laboratory results; the second laboratory value will be assessed based on the earliest value obtained  $\geq 24$  hours after the first value and may be based on central or local laboratory results.

**Table 5: Overview of Complete Thrombotic Microangiopathy Response**

		TMA Response Parameter
Complete TMA Response	Hematologic Response	

Normalization of platelet count without transfusion support during the prior 7 days

	Renal Response	

Normalization of LDH

Improvement in eGFR of <math>\geq 30\%</math> compared to baseline

Abbreviations: eGFR = estimated glomerular filtration rate; LDH = lactate dehydrogenase; TMA = thrombotic microangiopathy.

### **3.2.2. Hematologic Response**

Hematologic Response is defined as the normalization of platelets without transfusion support during the prior 7 days and the normalization of LDH.

### **3.2.3. Renal Response**

Renal Response is defined as an improvement in eGFR of  $\geq 30\%$  compared to baseline.

### **3.2.4. Loss of TMA Response**

For participants that meet the criteria for Complete TMA Response during the 26-week Treatment Period, Loss of TMA Response is defined as when the participant fails to meet the criteria for one or more components of TMA response at a subsequent visit during the 26-week Treatment Period. At least one parameter must fail to meet the response criteria at 2 separate assessments obtained at least 24 hours apart, and any measurement in between. The first laboratory value will be assessed based on central laboratory results; the second laboratory value will be assessed based on the earliest value obtained  $\geq 24$  hours after the first value and may be based on central or local laboratory results.

### **3.2.5. TMA Relapse**

For participants that meet the criteria for Complete TMA Response during the 26-week Treatment Period, TMA Relapse is defined as evidence of worsening hematologic and renal dysfunction due to TMA during the post-treatment follow-up period and requires treatment intervention, as determined by the Investigator.

## 4. STUDY DESIGN

### 4.1. Overall Design

This is a Phase 3, randomized, double-blind, placebo-controlled study of ravulizumab in addition to BSC in adult participants ( $\geq 18$  years of age) with TMA following a defined trigger. All participants must have acute kidney injury and a diagnosis of TMA, based on the protocol-defined criteria (ie, thrombocytopenia, microangiopathic hemolytic anemia, elevated LDH) occurring during the Screening Period and/or  $\leq 14$  days prior to start of the Screening Period, and which is associated with at least 1 trigger, such as autoimmune disease, infection, solid organ transplant, drugs, or malignant hypertension.

The study consists of an up to 2-week Screening Period, a 26-week randomized Treatment Period, and a 26-week Post-treatment Follow-up Period ([Figure 1](#)). Thus, the total treatment duration is 26 weeks and the total study duration is up to 54 weeks.

Participants will be screened for eligibility for up to 2 weeks during the Screening Period (and/or  $\leq 14$  days prior to start of the Screening Period for laboratory parameters). Approximately 100 adult participants will be randomized in a 1:1 ratio to receive either ravulizumab or placebo. Randomization will be stratified by baseline dialysis status and by primary trigger type.

During the Treatment Period, all participants will receive a weight-based loading dose of ravulizumab or placebo on Day 1, followed by weight-based maintenance doses of ravulizumab or placebo on Day 15 and then q8w thereafter ([Table 7](#)). All participants will receive BSC throughout the study as defined in Section [6.5](#).

During the Post-treatment Follow-up Period, participants may continue to receive BSC, at the discretion of the Investigator, and will be monitored for safety, TMA response, and clinical events of interest. If a participant meets criteria for TMA Relapse ([Section 3.2.5](#)) during the Post-Treatment Follow-up Period, the participant may be treated with BCS at the discretion of the Investigator.

The end of the study is defined as the last participant's last visit in the Post-treatment Follow-up Period.

### 4.2. Scientific Rationale for Study Design

A randomized, double-blind, placebo-controlled study design is selected to provide the most robust evidence of the efficacy of ravulizumab on TMA response, disease progression, and safety. Randomization minimizes the effects of baseline differences and confounding factors on the study endpoints. The use of a placebo comparator allows for a more accurate assessment of the true effects of treatment with ravulizumab.

Randomization will be stratified by baseline dialysis status and by primary trigger type using a dynamic allocation procedure. This dynamic randomization improves treatment balance when the number of strata is large compared to the total number of participants enrolled in the study.

The 26-week treatment duration was chosen to provide adequate time to assess safety, TMA response, and other efficacy endpoints after treatment with ravulizumab.

The study will limit the time between TMA presentation and treatment initiation, as well as the duration of dialysis prior to treatment initiation, to 2 weeks to assess the benefit of early intervention with ravulizumab on recovery of renal function. Because this study aims to establish efficacy with ravulizumab as an early therapeutic option for participants with complement-mediated TMA, in combination with removal of the trigger, the targeted study population will be participants who meet TMA criteria, but have more severe renal manifestations.

#### **4.2.1. Rationale for the Primary Endpoint**

The primary endpoint is Complete TMA Response during the 26-week randomized Treatment Period.

The renal component of the primary endpoint, improvement of  $\geq 30\%$  in eGFR, closely approximate with a  $\geq 25\%$  improvement in serum creatinine, which was a component of the primary endpoint in clinical studies of ravulizumab in treating patients with aHUS (Rondeau, 2020).

Measuring GFR through renal clearance of infused exogenous agents (eg, inulin) is the gold standard technique for assessing kidney function. Serum creatinine has been the most widely used surrogate for measured GFR, however, is confounded by endogenous factors including sex, ethnicity and age and exogenous factors such as creatinine assay variability and certain classes of medications that modulate renal handling of creatinine. This makes serum creatinine a poor surrogate for kidney function. The Chronic Kidney Disease Epidemiology Collaboration (CKD-EPI) equation for eGFR calculation is widely used for diagnosis and monitoring of kidney disease and was introduced because of known limitations of serum creatinine measurement (Florkowski, 2011). The CKD-EPI has been validated against measured GFR. The eGFR calculation uses sex, ethnicity, and age of the patient, some of the sources of variation when using the serum creatinine alone. However, as creatinine is effectively the only measured parameter in the eGFR equation, errors in the serum creatinine will produce errors in the eGFR. Serum creatinine has a low intra-individual coefficient of variation (CV) compared with the between individual CV. Thus, serum creatinine is not very sensitive as a marker of deteriorating renal function when an individual is compared to the population reference range. Indeed, it has been shown that the serum creatinine can remain within the population reference interval when the individual's GFR has decreased by 50% (Shemesh, 1985).

The renal component of the primary endpoint, improvement of  $\geq 30\%$  in eGFR, rather than complete recovery, is selected because renal repair after an insult is often maladaptive with inflammation, fibrosis, and vascular rarefaction leading to persistent cell and tissue malfunction and eventually chronic kidney disease (CKD). The frequency, severity, type, and duration of injury as well as the premorbid renal reserve seem to be risk factors for maladaptive repair (Venkatachalam, 2015). It is likely that maladaptive repair mechanisms will hinder complete recovery of renal function. In addition, patients with renal dysfunction are often continued on renal-protective medications, such as angiotensin-converting enzyme (ACE) inhibitors or angiotensin II receptor blockers (ARBs), which are known to reduce eGFR. Moreover, post-transplant patients are maintained on calcineurin inhibitors (CNIs), which are also known to reduce eGFR.

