## 1. PROTOCOL SUMMARY

### 1.1. Synopsis

**Protocol Title:** A Phase 3, Randomized, Double-blind, Placebo-Controlled, Multicenter Study to Evaluate the Efficacy and Safety of Ravulizumab in Adult Participants Who Have Thrombotic Microangiopathy Associated With a Trigger

**Short Title:** Phase 3 Study of Ravulizumab in Thrombotic Microangiopathy Associated With a Trigger

**Rationale:** The development of thrombotic microangiopathy (TMA) often follows activation of complement by a trigger. Such triggers include, but are not limited to, infection, drug exposure, autoimmune disease, transplant (solid organ or bone marrow), malignant hypertension, and pregnancy. The presence of one or more of these triggers is a consideration for the diagnosis of atypical hemolytic uremic syndrome (aHUS), a type of complement-mediated TMA. The first approved complement component 5 (C5) inhibitor, eculizumab, demonstrated efficacy in aHUS in clinical studies and in TMAs triggered by renal transplant in real-world data from the global aHUS registry. Multiple single-center studies have demonstrated the efficacy of eculizumab in treating a wide array of triggers. However, most studies assessing efficacy in this population are retrospective, single-arm/single-center experience, or fail to control for presentation severity or time to treatment. Thus, a randomized, controlled study is needed to assess C5 inhibition in TMA associated with a trigger.

Phase 3 studies with ravulizumab demonstrated efficacy in the treatment of TMA due to aHUS in adult and pediatric patients. In these studies, ravulizumab treatment achieved complete terminal complement inhibition resulting in Complete TMA Response, defined by normalization of hematologic parameters and improvement in renal function in the majority of patients. The study population included patients who presented with TMA after renal transplant or pregnancy, but excluded other triggers such as infection, drug exposure, and autoimmune disease.

The objective of this study is to investigate the efficacy and safety of ravulizumab administered by intravenous (IV) infusion compared to placebo in adult participants with TMA associated with a range of triggers.

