#### Disease Characteristics

4. TMA within  $\leq$  14 days prior to Screening is associated with at least 1 of the following triggers:
  - a. Autoimmune (lupus nephritis, systemic sclerosis associated TMA [SSc-TMA])
  - b. Infection
  - c. Solid organ transplant (eg, kidney, pancreas, liver, heart, small bowel)
  - d. Drugs
  - e. Malignant hypertension

5. Confirmation of all of the following laboratory findings during the Screening Period and/or  $\leq 14$  days prior to the start of the Screening Period:
  - a. Platelet count  $< 150,000/\mu\text{L}$
  - b. Lactate dehydrogenase  $\geq 1.5 \times \text{ULN}$  and hemoglobin  $\leq \text{LLN}$  (based on age and sex)
  - c. Acute kidney injury as defined by meeting 1 or more of the following criteria (for kidney transplant recipients, the pre-TMA value is based on post-transplant eGFR):
    - Acute decline in eGFR  $\geq 50\%$  from pre-TMA value (pre-TMA value must be  $\leq 12$  months prior to Screening)
    - New acute kidney injury with an eGFR  $\leq 30 \text{ mL/min}/1.73 \text{ m}^2$
    - New initiation of dialysis due to TMA requiring  $> 1$  session and for no more than 14 days prior to Screening

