4.3. Changes from Analyses Specified in the Previous Version of the SAP

Abbreviations: FACIT = Functional Assessment of Chronic Illness Therapy; PA2 = Protocol Amendment 2; SAP = statistical analysis plan; TMA = thrombotic microangiopathy

5. **DEFINITIONS**

5.1. **Primary Endpoint**

The primary efficacy endpoint of the study is complete TMA response during the 26-week randomized Treatment Period.

Complete TMA response is defined as normalization of hematologic parameters (platelet count and LDH) and \geq 30% improvement in estimated glomerular filtration rate (eGFR) from Baseline (Table 2).

Table 2:	Overview of Complete Thromb	ootic Microangiopathy Response
----------	------------------------------------	--------------------------------

		TMA Response Parameter
Complete TMA response	Hematologic response	 Normalization of platelet count (defined as platelet count ≥ 150000/µL) without transfusion support during the prior 7 days Normalization of LDH (defined as LDH
		\leq 1.5 × upper limit of normal)
	Renal response	• Improvement in eGFR of ≥ 30% compared to Baseline

Abbreviations: eGFR = estimated glomerular filtration rate; LDH = lactate dehydrogenase; TMA = thrombotic microangiopathy

If a participant is not on dialysis at Baseline, baseline eGFR will be defined as the last nonmissing assessment value prior to the start of study treatment. If a participant is on dialysis at Day 1, baseline eGFR will be set to 10 mL/min/1.73 m². If a participant is on dialysis during the entire 26-week randomized Treatment Period or through early discontinuation of study drug, then the change in eGFR will not be calculated.

For complete TMA response, participants must have met all 3 TMA response parameters simultaneously, with each component meeting the requirement at 2 separate assessments obtained at least 24 hours apart, and any measurement in between. The first laboratory value will be assessed based on central laboratory results; the second laboratory value will be assessed based on the earliest value obtained \geq 24 hours after the first value and may be based on central or local laboratory results.

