9.3.10. Serum Creatinine and eGFR

Serum creatinine measurements are not reliable with concurrent dialysis. Therefore, all serum creatinine values obtained while a participant is on dialysis will be excluded from all analyses. The eGFR rate will be imputed with a value of 10 (in mL/min/1.73 m²) while a participant is on dialysis. A participant will be considered on dialysis from the first day of dialysis through 5 days after the end of dialysis. A participant will be considered as not requiring dialysis at a specific post-Baseline time point if they have been dialysis free for at least 14 days prior to that time point. This rule will only be applied to postbaseline assessments of serum creatinine and eGFR.

The eGFR will be calculated based on creatinine using CKD-Epi equation in patients \geq 18 years of age:

eGFR = $141 \times \min(SCr/\kappa, 1)\alpha \times \max(SCr/\kappa, 1)-1.209 \times 0.993$ Age x 1.018 [if female] × 1.159 [if Black]

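### Does the ≥30% eGFR criterion need changing because it does not correspond to the ≥25% creatinine criterion that Protocol 4.2.1 says it approximates?

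*Protocol*

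**What the plan says.** Protocol 3.2.3 sets the renal threshold: "Renal Response is defined as an improvement in eGFR of" at least 30% compared with baseline. Protocol 4.2.1 then places this beside the criterion of the earlier programme. It says that the ≥30% improvement "in eGFR, closely approximate with a" ≥25% "improvement in serum creatinine, which was a component of the primary endpoint in clinical studies of ravulizumab in treating patients with aHUS". The next part of 4.2.1 gives a separate reason for asking for partial rather than full recovery: repair after kidney injury is often incomplete, and some maintenance drugs lower eGFR.

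Protocol 8.2.1 applies CKD-EPI to everyone. SAP 9.3.10 repeats this ("The eGFR will be calculated based on creatinine using CKD-Epi equation in patients" aged 18 or over) and prints the equation, with exponent -1.209 on creatinine/kappa when creatinine exceeds kappa.

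Dialysis is handled separately. SAP 5.1 states that for a participant on dialysis on Day 1 "baseline eGFR will be set to 10 mL/min/1.73" m², and SAP 9.3.10 states that "all serum creatinine values obtained while a participant is on dialysis will be excluded from all analyses".

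**The concern.** Within one person, age, sex and race cancel, so the printed equation fixes how a creatinine change maps to an eGFR change. The mapping does not return the pairing in 4.2.1. On the natural reading, the trial's renal threshold is easier to meet than the aHUS criterion beside which it is placed.

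What would be at stake is interpretation. The Protocol synopsis describes the aHUS results as "resulting in Complete TMA Response, defined by normalization of hematologic parameters and improvement in renal function in the majority of patients", so the endpoint name is shared. A reader who trusted 4.2.1 might set this trial's response rates beside the aHUS rates as if the renal criteria were matched. After early termination SAP 7.3.1 reports a rate and 95% confidence interval for each arm, with no between-arm test, which could make such a comparison more tempting.

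**Working it through.** **Inputs**
- Renal threshold: eGFR ratio 1.30 (Protocol 3.2.3).
- Creatinine criterion: 25% improvement (Protocol 4.2.1), read first as new/baseline = 0.75. SAP 9.3.5 expresses percent change relative to baseline, but that rule governs this trial and not the aHUS studies, so the reading is an assumption.
- Exponent: -1.209 for creatinine above kappa (SAP 9.3.10).

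**Can the stated pairing be reproduced?**

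The documents show no derivation, so three routes were tried.
1. Trial equation, eGFR ratio = (creatinine ratio)^-1.209:
   - 25% creatinine fall: 0.75^-1.209 = 1.416, a 41.6% eGFR rise.
   - 30% eGFR rise: 1 - 1.30^(-1/1.209) = 0.195, a 19.5% creatinine fall.
2. Simple reciprocal, eGFR proportional to 1/creatinine:
   - 25% fall: 1/0.75 = 1.333, a 33.3% rise.
   - 30% rise: 1 - 1/1.30 = 0.231, a 23.1% fall.
   - This roughly gives the stated pairing, but it is not the trial's formula.
3. Trial equation with improvement read as baseline/new = 1.25 (a 20% fall from baseline):
   - 1.25^1.209 = 1.310, a 31.0% rise. This matches 30% well.

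So 4.2.1 is inaccurate under route 1 and about right under routes 2 and 3.

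**Where route 1 applies**

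The -1.209 exponent holds while creatinine stays above kappa. At creatinine = kappa, the printed equation gives eGFR = 141 × 0.993^age for a male, non-Black participant, the lowest case:

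| Age | eGFR at kappa | Highest baseline for a 41.6% rise within the branch |
|---|---|---|
| 18 | 124.3 | 87.8 |
| 60 | 92.5 | 65.3 |
| 90 | 74.9 | 52.9 |

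For ages up to 90 the conversion is therefore exact for a Day 1 baseline up to about 53. One entry route in inclusion criterion 5c is "New acute kidney injury with an eGFR" of 30 or less. That does not guarantee a Day 1 baseline below 53: eligibility results may come from up to 14 days before Screening, whereas baseline is the last value before treatment. Another 5c route, a decline of at least 50%, has no absolute ceiling.

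**Size on the eGFR scale, not on dialysis on Day 1**
- Baseline 15: 15 × 1.30 = 19.5 qualifies; a 25% creatinine fall would mean 15 × 1.416 = 21.2.
- Baseline 30: 30 × 1.30 = 39.0, against 30 × 1.416 = 42.5.

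**On dialysis on Day 1**

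Baseline is fixed at 10, so the threshold is 10 × 1.30 = 13. There is no usable baseline creatinine and no conversion to make.

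**Does anything downstream use the 25%?**
- Endpoint definition (Protocol 3.2.1 and 3.2.3, SAP 5.1): uses 30% eGFR only.
- Sample size (Protocol 9.2, SAP 9.2): assumes 35% and 70% response. The sources cited there do not include the aHUS study cited in 4.2.1.
- Analyses (SAP 7.3): no creatinine criterion and no comparison with another trial. The SAP does not mention the 25% figure at all.

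**The case for a change.** The best case for acting is this. A 30% eGFR rise against 41.6% is not close on any ordinary use of the word. The comparison with creatinine is the only text in 4.2.1 that bears on the number 30, since the later paragraph explains only why full recovery was not required. With between-arm inference dropped and per-arm rates reported, outside comparison becomes likelier, and correcting one sentence costs almost nothing.

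Part of this stands. On the fall-from-baseline reading the sentence is inaccurate, and a reader should not treat the two renal criteria as matched.

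The rest is weaker. Section 4.2.1 does not say that 30% was derived from the creatinine criterion; it offers a qualitative comparison. The discrepancy depends on a definition held in a source outside the documents, and one other reading removes it. Participants on dialysis on Day 1 are outside the point altogether, and Protocol 4.2.2 puts dialysis at presentation at up to 40% or more. The possible misreading is also indirect, because the synopsis gives the aHUS renal result without any threshold. A disclaimer in the SAP would rebut a claim that the SAP never makes. A listing of participants with a 25% creatinine fall, among 16 enrolled, would answer no question that the trial asks.

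**Conclusion.** This is a clerical inaccuracy in a rationale sentence, with no gain from changing the plan. If improvement means a fall from baseline, the threshold corresponds to about a 19.5% creatinine fall rather than 25%, a gap of 5.5 percentage points on the creatinine scale (25 - 19.5), or 11.6 points on the eGFR scale (41.6 - 30). If improvement means baseline/new = 1.25, the gap on the eGFR scale is about 1 point (31.0 - 30). Either figure applies only to participants not on dialysis on Day 1 whose creatinine stays above kappa. The number falling between the two thresholds cannot be estimated from the documents.

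The ≥30% definition is explicit, is computed the same way in both blinded arms, and would be kept in any case. Power, derivations, analysis sets and reported results are the same whether or not the sentence is reworded. Anyone setting these response rates beside the aHUS studies should check the renal definitions at source, as with any comparison between trials.

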#### **4.2.2. Rationale for the Secondary Endpoints**

Time to achieve Complete TMA Response during the 26-week Treatment Period will provide prescribers with additional guidance to evaluate and characterize efficacy of ravulizumab treatment. In addition, given the fact that the resolution of the different TMA components may occur at different time points after treatment initiation, and that some participants may experience partial response, additional key secondary endpoints including the proportion of participants that achieve the individual components of the Complete TMA Response definition, as well as the time to achieve each of them, will be evaluated to fully characterize the potential benefit of ravulizumab treatment. The proportion of participants that achieve an increase of  $\geq 1$  gram/dL and  $\geq 2$  grams/dL in hemoglobin will also be assessed.

Complement-mediated TMA is a multisystem complication with prominent kidney involvement. Literature shows that up to 40% or more of patients with complement-mediated TMA are on dialysis at presentation (Le Clech, 2019). Therefore, secondary endpoints to assess change in dialysis status as well as change in eGFR have been chosen.

